### **XI. DATA ANALYSIS**

**a. Plan of Analysis.** Based on previous research and our preliminary data, we anticipate  $\geq 18\%$  of patients will be non-adherent to screening guidelines. As such, we will enroll 450 patients to identify  $\geq 90$  non-adherent patients. To test **Specific Aim 1 - Hypotheses 1A/1B**, we will use (a) a one sample test of improvement in adherence at follow-up and (b) a two-sample comparison of post-intervention adherence across intervention conditions. These analyses will allow us to establish preliminary effect sizes for powering the subsequent NIH submission. The first test will compare % adherent at follow-up against a null value of 15% improvement (i.e., % of non-adherent subjects who would become adherent over 150 days without intervention). We think this is an unrealistically high null value, but it was chosen to avoid overestimating the impact of the study interventions. Using this null value, a one-tailed test with  $\alpha=0.05$ , and  $\geq 90$  non-adherent subjects across conditions, we will have power of 0.80 to observe improvement as small as 10% over the null (40% relative improvement). The second test will use  $\chi^2$  to compare conditions. Given a one-tailed test with  $\alpha=0.10$  and 45 non-adherent subjects in each condition, we will have power of 0.70 to observe a difference as small as 24% in adherence at follow-up. More importantly, we will establish a 95% confidence interval around the overall improvement rate (across conditions) with  $\leq 10.4\%$  margin of error and intervention specific rates of improvement with  $\leq 14.8\%$  margin of error. These intervals will allow us to calculate power for the subsequent trial under expected, ideal, and worst-case scenarios. Patients lost to follow-up will be considered intervention failures (i.e. non-adherent) in accordance with intention-to-treat principles. In order to test **Specific Aim 2 - Hypothesis 2**, we will use hierarchical, multinomial logistic regression to predict adherence at baseline. Given our sample size and an expected adherence rate of 0.80, at  $\alpha=0.05$ , we will have power  $\geq 0.70$  to observe odds ratios as small as 1.33. Any covariates demonstrating a  $p$ -value  $\leq 0.10$  will be addressed when refining the interventions for the subsequent NIH trial. **Specific Aim 3** is focused on the qualitative feedback data collected at the 150-day follow-up call. Qualitative data analysis of the feedback data will include open and axial coding under Grounded Theory principles examined in the context of subject demographic characteristics. The codes/concepts that emerge from these data will be examined in the context of the demographic characteristics of the subjects providing feedback. Results will then be used to refine the intervention protocols for the subsequent efficacy trial.

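### The 0.80 power stated for the one-sample test is a normal approximation; at n=90 the usual versions of the test attain about 0.76, and the plan does not name the version

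*Combined protocol and SAP*

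**What the plan says.** Section XI.a, Plan of Analysis, tests Hypothesis 1A with "a one sample test of improvement in adherence at follow-up". The reference value is fixed: "The first test will compare % adherent at follow-up against a null value of 15% improvement". The sidedness, level and sample size are given as "a one-tailed test with $\alpha=0.05$ , and $\geq 90$ non-adherent subjects across conditions". On these inputs the plan states "we will have power of 0.80 to observe improvement as small as 10% over the null". Losses stay in the denominator: "Patients lost to follow-up will be considered intervention failures (i.e. non-adherent").

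The section does not say whether the test is exact, mid-p, score or Wald, or whether a continuity correction is used. It does not say which formula produced the power figure, and it gives no rejection count.

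**The concern.** The outcome is a count of adherent women out of n, so any version of the test reduces to a whole-number cut-off. A smooth power formula can assume a cut-off that falls between two counts, and no test can use such a cut-off. If the usual versions share one cut-off at the planned n, they share one true power, and the stated figure should be compared with that.

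What is at stake is the chance of missing a true rate of 25%: about 24% rather than the 20% implied. There is also a smaller point. With the version unnamed, the cut-off for an achieved n other than 90 could be settled after the data are seen.

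**Working it through.** **Inputs, all from Section XI.a.** Null p0 = 0.15. Alternative p1 = 0.15 + 0.10 = 0.25. One-tailed alpha 0.05, z = 1.645. n = 90, the stated minimum. Women lost to follow-up count as failures, so n is not reduced.

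The plan also glosses the improvement as 40% relative, which does not match 10 points over 15% (10/15 = 67%). I take 25% as the intended alternative because it reproduces the stated power. A rate of 21% (15% × 1.4) would give only 0.48 by the same formula.

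**Step 1: reproduce the plan's figure.**

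Power = Φ{[(p1 − p0) − z·√(p0(1−p0)/n)] / √(p1(1−p1)/n)}

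- √(0.15 × 0.85/90) = 0.03764
- √(0.25 × 0.75/90) = 0.04564
- (0.10 − 1.645 × 0.03764)/0.04564 = 0.8345
- Φ(0.8345) = 0.798, which rounds to the stated 0.80

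The cut-off implied by this formula is 0.15 + 1.645 × 0.03764 = 0.2119, or 19.07 women out of 90. That lies just above 19, so the first count that can reject is 20.

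**Step 2: find the cut-off for each version at n=90 (one-sided p-values).**

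| Version | 19 of 90 | 20 of 90 |
|---|---|---|
| Score z, uncorrected | 0.0522 | 0.0275 |
| Score z, continuity-corrected | 0.070 | 0.038 |
| Wald z | 0.078 | 0.0497 |
| Mid-p | 0.059 | 0.034 |
| Exact binomial | 0.0745 | 0.043 |

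Every version in the table rejects from 20 and none at 19. The arcsine and likelihood-ratio versions do the same. A one-sample t version has p = 0.052 at 20, so it needs 21.

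**Step 3: binomial operating characteristics at n=90.**

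| Reject at | Attained alpha, P(X ≥ r given 0.15) | Power, P(X ≥ r given 0.25) |
|---|---|---|
| 19 or more | 0.0745 | 0.835 |
| 20 or more | 0.0434 | 0.764 |
| 21 or more | 0.0240 | 0.681 |

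Solving P(X ≥ 20 given p) = 0.80 at n = 90 gives p = 0.256, an improvement of 10.6 points over the null.

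**Step 4: n from 90 to 100, since 90 is a minimum.** Each cell gives the cut-off, attained alpha and power at 25%.

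| n | Exact test | Uncorrected score test |
|---|---|---|
| 90 | 20; 0.043; 0.764 | 20; 0.043; 0.764 |
| 91 | 20; 0.048; 0.782 | 20; 0.048; 0.782 |
| 92 | 21; 0.030; 0.722 | 20; 0.053; 0.799 |
| 93 | 21; 0.034; 0.741 | 20; 0.058; 0.814 |
| 94 | 21; 0.037; 0.759 | 20; 0.064; 0.829 |
| 95 | 21; 0.041; 0.777 | 20; 0.070; 0.843 |
| 96 | 21; 0.046; 0.794 | 21; 0.046; 0.794 |
| 97 | 22; 0.029; 0.737 | 21; 0.0503; 0.809 |
| 98 | 22; 0.032; 0.755 | 21; 0.055; 0.824 |
| 99 | 22; 0.036; 0.772 | 21; 0.061; 0.838 |
| 100 | 22; 0.039; 0.789 | 21; 0.066; 0.851 |

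The score test passes 0.80 at n = 93–95 and 97–100, and mid-p does so at 93 and 97–99. At each of these n the attained alpha is above 0.05. The exact test first reaches 0.80 at n = 101 (22 or more; 0.804) and stays at or above it from n = 110.

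**The case against.** The strongest reply is that nothing was miscalculated. The textbook formula on the plan's own inputs gives 0.798, and the plan promises neither an exact test nor an exact power method. This stands: a reader who saw only the 0.764 might infer a slip in the sponsor's arithmetic, and the document does not support that.

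A second reply is that n = 90 is an unlucky point. The plan says at least 90, and the final number is random: it depends on how many of the 450 enrollees are non-adherent and on how uncertain women are reclassified (Section II.a). Across n = 90 to 100 the uncorrected score test averages about 0.81, and at n = 88 and 89 it gives 0.804 and 0.820. This stands in part. A reader might infer that no version of the test reaches 0.80 anywhere near the planned size, and Step 4 shows that to be false. But where the score test reaches 0.80 in that range, it does so at an attained level of 0.0503 to 0.070 against the declared 0.05. At n = 90, the size the plan powers on, it does not reach 0.80.

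A third reply is proportion. The plan introduces its confidence intervals as the more important output, and no enrolment target or go/no-go rule turns on 0.76 versus 0.80. This stands, and it limits the point to a minor one.

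**Conclusion.** The point holds as a minor matter of accurate statement. For 25% versus 15% at one-tailed 0.05, the stated 0.80 is a sound normal approximation. At exactly n = 90 the score, Wald, mid-p and exact tests all attain 0.764, a shortfall of 3.6 points, with attained alpha 0.043. Above 90 the power depends on a choice the plan has not made: 0.72 to 0.79 for the exact test up to n = 100, and 0.76 to 0.85 for the uncorrected score test, which goes over the declared level wherever it reaches 0.80.

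This rests on reading the improvement as 10 percentage points and on n = 90. The second assumption is itself doubtful: the plan's anticipated 18% of 450 is 81 women, not 90. At n = 81 the normal approximation gives 0.765 and the exact test (19 or more) 0.667, so a shortfall in numbers would matter more than discreteness does.

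**What to change.** In Section XI.a, replace the unqualified figure with one of two statements. Either: power is approximately 0.80 by normal approximation, with 0.76 attained at n = 90 for 25% versus 15%. Or: power is 0.80 at n = 90 for a 10.6-point improvement. In the same sentence, name the version of the test and say that the cut-off follows from the achieved n (20 or more if n = 90).

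Settle the expected number of non-adherent women first, or at the same time, because the attained figure changes with n and a value for n = 90 would otherwise soon be out of date.

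The cost is one sentence and a slightly less favourable power figure. No change to sample size, procedures or participant contact is needed.

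### Two Aim 1 figures do not follow from their stated inputs: the 24-point detectable difference should be about 16 to 22 points, and the 40% relative improvement should be 67%

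*Combined protocol and SAP*

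**What the plan says.** Both figures are in Section XI (Data Analysis), a. Plan of Analysis, under Specific Aim 1.

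- **A versus B.** The plan describes "a two-sample comparison of post-intervention adherence across intervention conditions" by chi-square. The inputs are introduced with "Given a one-tailed test with" alpha 0.10 and "45 non-adherent subjects in each condition". The result given is "we will have power of 0.70 to observe a difference as small as 24% in adherence at follow-up". No Intervention A rate is stated for this calculation, and nothing says whether a continuity correction or Fisher's test would be used.
- **One-sample test.** Adherence at follow-up is compared with "a null value of 15% improvement", meaning the share "of non-adherent subjects who would become adherent over 150 days without intervention". With a one-tailed alpha of 0.05 and at least 90 women, the plan claims power 0.80 for "improvement as small as 10% over the null (40% relative improvement").

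Of the Aim 1 analyses the section says: "These analyses will allow us to establish preliminary effect sizes for powering the subsequent NIH submission".

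**The concern.** A power statement should be reproducible from its own inputs. With 45 per arm and a lenient one-tailed alpha of 0.10, 24 points is a large difference to be detectable with only 0.70 power. If the figure is wrong, a reader cannot tell which input slipped. One possibility is the sidedness of the test, which would also affect how the trial result is judged.

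The relative figure fails on sight, since 10 points on a base of 15% cannot be a 40% gain. A reader who took 40% as the detectable effect would be thinking of a rise from 15% to 21%, for which this pilot has much less than 0.80 power.

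**Working it through.** **Inputs, all from Section XI.a.** Two-sample test: one-tailed alpha 0.10 (z = 1.2816), n = 45 per arm, power 0.70 (z = 0.5244), difference d = 0.24. One-sample test: null 0.15, one-tailed alpha 0.05 (z = 1.6449), n = 90, power 0.80, difference 0.10. Women lost to follow-up count as failures, so n is not reduced for dropout. The Intervention A rate p1 is not given. I scanned 1% to 50%, and higher rates mirror lower ones. I treat 15% and above as the main range because 15% is the only follow-up rate in the plan.

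**1. A versus B**

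Power = Φ{[d − 1.2816·√(2p̄(1−p̄)/n)] / √([p1(1−p1)+p2(1−p2)]/n)}, where p2 = p1 + d and p̄ is the mean of p1 and p2.

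The plan's own difference of 24 points:

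- 15% vs 39%: (0.24 − 1.2816 × 0.0936) / 0.0901 = 1.332, so power is 0.909.
- 38% vs 62%, close to the least favourable pair: (0.24 − 1.2816 × 0.1054) / 0.1023 = 1.025, so power is 0.847.

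The stated 0.70 does not reproduce. The continuity-corrected version replaces n by n(1 − 1/(nd))², which is 37.05 when n = 45 and d = 0.24. The exact versions add up binomial probabilities over all outcomes where the test rejects.

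| p1 | Normal approx. | Exact chi-square | Continuity-corrected normal | Fisher |
|---|---|---|---|---|
| *Power at 24 points* | | | | |
| 15% | 0.909 | 0.913 | 0.861 | 0.864 |
| 25% | 0.867 | 0.875 | 0.812 | 0.827 |
| 38% | 0.847 | 0.829 | 0.790 | 0.773 |
| *Points detectable at power 0.70* | | | | |
| 5% | 11.8 | 11.2 | 14.6 | 14.0 |
| 15% | 15.9 | 15.6 | 18.4 | 18.4 |
| 25% | 17.9 | 17.4 | 20.3 | 19.7 |
| Largest over all rates | 18.9 | 19.6 | 21.1 | 21.7 |

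No variant reaches 24 at any rate. Conversely, 24 points at power 0.70 needs 22 per arm (15% vs 39%) to 28 (38% vs 62%) uncorrected, or 30 to 36 with a continuity correction or Fisher's test. The plan has 45.

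Taking the 18% non-adherence rate literally gives 0.18 × 450 = 81 women, or 40.5 per arm. The largest detectable difference is then 19.9 points (22.4 continuity-corrected), still below 24.

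About 24 points does appear if one stated input is changed:

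- two-sided alpha 0.10, continuity-corrected, p1 = 25%: 24.1 points;
- two-sided alpha 0.05, uncorrected, p1 = 20%: 24.3 points;
- one-tailed alpha 0.10, continuity-corrected, p1 = 30%: power at 24 points is 0.799, so the figure would fit if 0.70 should have read 0.80.

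Several slips fit, so the cause cannot be inferred.

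**2. One-sample label**

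Power = Φ{[(p1 − 0.15) − 1.6449·√(0.15·0.85/90)] / √(p1(1−p1)/90)}, where p1 is now the follow-up rate under the alternative.

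- 25%: (0.10 − 0.0619) / 0.0456 = 0.834, so power is 0.798. The claim of 10 absolute points at power 0.80 reproduces.
- Relative gain: 0.10/0.15 = 0.667. The printed 40% equals 0.10/0.25, which divides by the alternative instead of the null.
- A true 40% gain is 0.15 × 1.4 = 0.21: (0.06 − 0.0619) / 0.0429 = −0.045, so power is 0.48. Power 0.80 would need [(1.6449·√0.1275 + 0.8416·√0.1659)/0.06]² = 240.3, or 241 women.
- A null of 25% would make 40% correct (25% to 35%), but power would then be 0.69, not 0.80. The label is therefore what is wrong.

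**The case against.** The strongest reply is that nothing depends on either figure. Enrolment of 450 is justified by the yield of at least 90 non-adherent women, not by the 24 points. Power for the next trial is to be calculated from the observed rates and their 95% confidence intervals. The stated worst-case margins hold: 1.96·√(0.25/90) = 10.3 points and 1.96·√(0.25/45) = 14.6 points, against stated limits of 10.4 and 14.8. The plan never claims power for 15% against 21%. This stands, and it keeps the point minor.

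A second reply is that 16 to 22 points depends on an Intervention A rate of about 15% or more, which the plan does not state; it even calls 15% unrealistically high without intervention. That is correct, but lower rates move the answer further from 24, as the 5% row shows.

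A third is that 24 may be the right number and one-tailed the wrong word, because an ordinary chi-square test is non-directional. That is possible. It is a reason not to replace 24 with 19 before the inputs have been checked, but it does not make the sentence correct as written.

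**Conclusion.** Both figures are wrong as written.

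- With the stated alpha, sidedness, sample size and power, the detectable A-versus-B difference is about 16 to 22 points for Intervention A rates of 15% or more, and smaller below that. The plan states 24, so it understates what the test can detect by about 2 to 8 points. This holds for every rate and test variant examined.
- The relative improvement is 67%, not 40%.

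The severity is minor. If the stated inputs are right, the first error is conservative and the trial is not underpowered because of it. The second is confined to a label beside a correct absolute effect. The documents do not show which A-versus-B input slipped.

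**What to change.** 1. Go back to the A-versus-B calculation and reconcile alpha, sidedness, n, power and difference. If one-tailed 0.10 and 45 per arm stand, restate the detectable difference as about 19 points at 0.70 power, or keep 24 points and give power as about 0.85. Both are least-favourable-rate values for the uncorrected chi-square. If another input was mistaken, correct that one instead.
2. Add one sentence giving the assumed Intervention A rate and saying whether the test is uncorrected, continuity-corrected or Fisher's.
3. Change the relative improvement in the one-sample statement from 40% to 67%.

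The cost is two corrected figures and one added sentence. Enrolment and timeline do not change, and neither does the planned test unless the check shows that its sidedness was misdescribed.

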**Figure 1. Project Workflow**

After consent, enrollees will complete a ~10-minute computer-adaptive questionnaire, administered at the bedside on a tablet computer by the EDRA to determine adherence to current USPSTF recommendations for cervical cancer screening. The REDCap adaptive screening tool used will be identical to that which was used to gather our preliminary data. The enrollment process will categorize study participants into three groups: adherent, uncertain, or non-adherent (Figure 2). Women found to be adherent will be notified and their participation will conclude (i.e. no follow-up will be performed). Women found to be in the uncertain or non-adherent groups will then be randomized into one of two intervention conditions. Randomization will be automated in the REDCap survey instrument. All women found non-adherent will be referred to their usual care provider. If the patient does not have a usual provider of women's healthcare, she will be referred to UR WHP to receive appropriate screening. [name] (co-I) will maintain an expedited referral pathway to UR WHP for these subjects. [name] or one of the other health care providers at WHP will conduct the screening test. Women for whom adherence is uncertain (e.g. unsure, unable to remember) will be referred to their usual care provider or to UR WHP to confirm their adherence status. If, upon follow-up, the patient was confirmed adherent, she will be retroactively classified as adherent at baseline (though her uncertain status at screening will be retained in the dataset for potential secondary analyses). If confirmed non-adherent, the patient will be retroactively classified as non-adherent at baseline (with initial uncertainty retained). If the patient did not contact a provider to confirm adherence status (and did not remember her status in the 150 day interim), she will remain classified as uncertain.

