**b. Description of Interventions.** The proposed study pilots two interventions aimed at improving adherence to guidelines by encouraging screening outside of the ED. **Intervention A** only involves screening for adherence status and referral of uncertain and non-adherent patients for screening and/or confirmation of status and screening. **Intervention B** follows the Screening, Brief Intervention, and Referral to Treatment (SBIRT) model popularized in the substance use literature in the ED . The three components of the TPB intervention will be delivered via a series of text messages to mobile phones. Patients will receive a total of three text messages at 30-day intervals between the ED index visit and telephone follow-up survey at

150 days. Each text message will include a statement directed towards one of the TPB predictors of behavioral change intentions (Table 1) accompanied by a reminder to schedule cervical cancer screening with their primary provider or the WHP. Attitudes regarding cervical cancer screening will be addressed by emphasizing its efficacy for preventing morbidity.

Table 1 – Theory of Planned Behavior Texts to Participants in Intervention B

Element of the TPB	TPB portion of text	Scheduling portion of text
Attitudes about Screening	“Regular screening for cervical cancer is an extremely effective way to prevent cancer or identify early stages of cancer that can be effectively treated”	
Subjective Norms about Screening	“Over 80% of women across the country stay up-to-date with cervical cancer screening guidelines.”	Schedule cervical screening by calling your usual women’s health provider at {Participant-specific phone number} or with UR Women’s Health Practice at [contact]
Perceived Behavioral Control over Obtaining Screening	“Pap tests are available, without cost to you, at your women’s health provider or at the UR Women’s Health Practice.”	

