Subjective normative beliefs about screening will be addressed by emphasizing the preponderance of adherence to guidelines in the population. Perceived behavioral control over obtaining cervical screening will be addressed by discussing the accessibility and negligible financial burden of Pap tests. Women who have their own women’s health providers will be instructed to follow-up with these providers or utilize UR WHP, whichever they prefer. To facilitate patient follow through, the message will include hyperlinks to the telephone numbers of the patient’s women’s health care provider (if known) and the WHP.

**c. Follow Up.** All enrollees in the non-adherent and uncertain groups will receive a follow-up call at 150 days (Figure 3). The project coordinator will contact each of these participants by telephone for a brief REDCap questionnaire to determine if they underwent screening, if they learned that they did not require screening, and what barriers they perceived in getting screened or clarifying their adherence. Qualitative feedback regarding perceptions of the interventions will also be solicited from study participants in order to refine the interventions for future study. Relevant domains of feedback will include challenges to adhering with screening guidelines, comfort level with the intervention content discussed in the ED, which TPB message(s), if any, were perceived as most generative of intention to engage in cervical cancer screening, and participant recommendations for intervention revision. Telephone numbers will be confirmed in the ED during enrollment by the EDRA performing the enrollment (e.g., calling patient’s phone to be certain the number is correct), and up to 3 calls will be made to each of these patients to limit unnecessary attrition.

Study team members will use the EPIC medical record to confirm self-reported screening activities among the subjects successfully contacted at follow-up and who report a women’s health provider associated with UR Medicine. No confirmation will be sought among subjects reporting cervical screening with providers outside of the UR Medicine system.

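### A UR Medicine screening record cannot count as success for a woman the study fails to reach by phone, so the overall improvement rate may be set too low.

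*Combined protocol and SAP*

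**What the plan says.** - **Missing outcomes.** Section XI.a: "Patients lost to follow-up will be considered intervention failures (i.e. non-adherent) in accordance with intention-to-treat principles".
- **Source of the outcome.** Section II.c obtains it from a telephone questionnaire at 150 days: "up to 3 calls will be made to each of these patients to limit unnecessary attrition".
- **Records for reached women.** Section II.c uses EPIC to "confirm self-reported screening activities among the subjects successfully contacted at follow-up", and only where they name a UR Medicine provider. Section XI.b likewise uses UR WHP records and eRecords to corroborate self-reports.
- **Records for everyone.** Section II.c also plans a limited review of UR Medicine records for all enrolled women over a five-year period. The date from which the five years are counted is not given. The stated uses are comparison with self-report and assessing whether women know their screening schedule.
- **Uncertain women.** Section II.a has its own rules. For a woman confirmed adherent: "If, upon follow-up, the patient was confirmed adherent, she will be retroactively classified as adherent at baseline". For a woman with no confirmation: "she will remain classified as uncertain".
- **Identifiers.** Section V.a has them deleted once follow-up is complete.

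**The concern.** The study sends women without a usual provider to a clinic whose records it can read: "she will be referred to UR WHP to receive appropriate screening". A woman could attend that clinic, have a documented screen within the 150 days, miss the calls, and be analysed as non-adherent. The study may hold, or could readily obtain, evidence of her success and has no rule for using it.

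Section XI.a ranks the confidence intervals for the improvement rates above the hypothesis tests, because they will be used to calculate power for the next trial. Scoring documented successes as failures moves the centre of the overall interval down without changing its planned width, so a reader of the interval would not see the problem.

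**Working it through.** **Inputs from Section XI.a.** Null 15%, alternative 25% (10 points above the null), n = 90, one-tailed α = 0.05; margins of error of at most 10.4% overall and 14.8% per arm.

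**Assumptions, because the documents give no figures.** Loss L = 10%, 20% or 30%. Ratio r of the screening rate in unreached women to that in reached women = 0, 0.5 or 1. Share f of unreached women's screens found in UR Medicine records = 0 or 0.5. The true overall rate is held at 25%.

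**Step 1: reproduce the stated power.** Power = Φ{[(p − 0.15) − 1.645·√(0.15·0.85/90)] / √(p(1 − p)/90)}. At p = 0.25 this is Φ{(0.10 − 0.0619)/0.0456} = 0.798, which matches the stated 0.80. Here p is the rate among all 90 women after lost women are scored as failures.

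**Step 2: precision.** The worst-case margin is 1.96·√(0.25/n): 10.33% at n = 90 and 14.61% at n = 45. Both are within the stated limits, and failure scoring leaves n unchanged.

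**Step 3: what failure scoring misses.** The rate in reached women is q = 0.25/[(1 − L) + L·r]. The failure-scored rate is q(1 − L), and the missed share is q·r·L. Example with r = 0.5 and L = 20%: q = 0.25/0.90 = 27.8%; scored rate 22.2%; missed 2.8 points, or 2.5 of 90 women.

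| r | Missed points at L = 10/20/30% | Power, phone-only rate | Power if f = 0.5 |
|---|---|---|---|
| 0 | 0 / 0 / 0 | 0.80 / 0.80 / 0.80 | unchanged |
| 0.5 | 1.3 / 2.8 / 4.4 | 0.71 / 0.59 / 0.44 | 0.76 / 0.71 / 0.64 |
| 1 | 2.5 / 5.0 / 7.5 | 0.62 / 0.39 / 0.18 | 0.72 / 0.62 / 0.51 |

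The missed points count all screens in unreached women. Records can recover only the fraction f of them. For f = 0.5 the scored rate is q(1 − L) + 0.5·q·r·L.

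**Step 4: can using records bias A versus B?** Arm B's texts carry a message "accompanied by a reminder to schedule cervical cancer screening with their primary provider or the WHP", so every woman in B is pointed to UR WHP, whereas the referral in Section II.a names that clinic only for women without a usual provider. Record capture may therefore be higher in B. With equal true rates and equal loss in both arms, the spurious gain for B is q·r·L·(f_B − f_A):

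- f of 40% in A and 60% in B: 0.3 / 0.6 / 0.9 points at r = 0.5, and 0.5 / 1.0 / 1.5 points at r = 1.
- The extreme of 0% against 100%: 1.3 / 2.8 / 4.4 points at r = 0.5, and 2.5 / 5.0 / 7.5 points at r = 1.

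These compare with the 24-point difference in Section XI.a, which is tested one-tailed at α = 0.10.

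**The case against.** **Failure scoring is a legitimate choice.** It is prespecified, applies the same rule to both arms, keeps every randomised woman, and suits a plan that sets a deliberately high null so as not to overstate the effect. This stands as a defence of the rule for women whose outcome is unknown. It does not justify overriding a documented outcome.

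**The reading is partly inferred.** Loss to follow-up is not defined, and equating it with not being reached by phone is an inference. Section II.c supports it, since the call is the only planned follow-up contact. Using the all-enrollee review for the outcome is unstated rather than ruled out. One sentence from the sponsor could settle both.

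**The fix may favour the hypothesis.** Step 4 shows that this objection stands. Records should not replace the planned phone-only comparison of the arms.

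**The fix may cost more than wording.** If the five years were meant as a look-back from enrolment, the 150 days after the visit would be additional abstraction. This also stands, as a modest cost.

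**A stronger reading to avoid.** A reader might infer from the lower powers in the table that the stated 0.80 is overstated. The documents do not support that: the figure reproduces for 25% among all 90 women after failure scoring. The lower values arise only if 25% is taken as the true rate and some unreached women were screened.

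**Conclusion.** The concern holds as a cheap improvement, not as an error in the plan. As written, and if lost means not reached by phone, a UR Medicine screen in an unreached woman is counted as non-adherence, which lowers the overall improvement rate and the centre of its interval. The amount cannot be fixed from the documents. It is 0 to 7.5 points at losses up to 30%, provided unreached women are screened no more often than reached women, and about 1 to 4 of 90 women in the half-as-often case. If no unreached woman was screened, there is no bias.

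Nor should a reader infer that planned precision is lost, because the margins in Step 2 are intact. The net direction of error is not certain either: self-reports of screening outside UR Medicine are not verified and could push the rate up.

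**What to change.** 1. State in Section II.c that the record review also covers index visit to day 150 for every randomised woman, reached or not, is done the same way in both arms, and is completed before the identifier deletion in Section V.a.
2. For the overall improvement rate and its interval, score a self-reported or recorded screen in that window as success. Keep failure scoring for women with neither. Report the phone-only failure-scored rate beside it.
3. For A versus B, keep the phone-only failure-scored comparison as planned. Add the record-augmented comparison as a prespecified sensitivity analysis, with the number of record-only successes in each arm.
4. Leave uncertain and over-referred women to the existing provisions of Sections II.a and XI.b, and remove no further women from the denominator. Such removal would depend on who is reached, and with 88 women the worst-case overall margin is 1.96·√(0.25/88) = 10.45%, above the stated 10.4%.
5. If a power sentence is added, say that 0.80 applies to a phone-only failure-scored rate of 25% among 90 women.

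The cost is SAP wording, a date window and timing for a review already planned for the same women, and some extra chart abstraction if that review was meant to look back from enrolment. Screens outside UR Medicine in unreached women would still be missed.
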